### **Expected duration of the project:**

Approximately three years depending on the number of patients who meet inclusion criteria.

### **Hypothesis:**

The dose of propofol necessary to reach an optimal anesthetic depth could be reduced if the time since the administration of fentanyl is prolonged, thus avoiding the pre-intubation hypotension and postintubation hypertension.

### **Objectives:**

#### **General**

To determine if, by increasing the time elapsed between the administration of fentanyl and propofol and decreasing the dose of the latter, fewer hemodynamic changes related to orotracheal intubation occur.

#### **Specifics**

- Assess whether the patient's age is a determining factor in hemodynamic variations dependent on time-dose.
- Evaluate hemodynamic variations after anesthetic induction according to the dose of propofol and the time since administration of fentanyl.
- Determine if hypertensive patients and those treated with antihypertensives or heart rate regulating drugs suffer greater hemodynamic variations during anesthetic induction.
- Analyze if the time is delayed from the administration of fentanyl delays the moment until reaching the optimal anesthetic depth.
- Determine if premedication with benzodiazepines alters the time to reach hypnosis.

### **Subjects and Methods**

## Subjects

All adult patients scheduled for surgery that, under the care of the same anesthesiologist, require general anesthesia with tracheal intubation, that meet inclusion criteria and accept participation and sign written consent.

- Inclusion criteria:

- Older than 18 years
- Requiring general anesthesia with tracheal intubation
- Same operator
- Accepting participation and signing written consent

- Exclusion criteria

- Cardiac surgery
- Hemodynamic unstable patients: systolic blood pressure (SBP)  $\leq$  90 mmHg with clinical signs of low cardiac output (impaired state of consciousness, diuresis  $<0.5$  ml/kg/h, central venous saturation  $<60\%$  with normal arterial saturation or lactate  $>3$  mmol/l).
- Increased risk of bronchoaspiration: absence of fasting for 6 hours for solid foods and 2 hours for clear liquids or presence of pathologies that imply an absence of gastric emptying.
- Predictors, known or unexpected difficult airway.
- Airway management with other supraglottic devices.
- Known allergy to anesthetic drugs (muscle relaxants, hypnotics, etc.), egg or soy proteins.

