## Methods

### Design

This is a prospective and randomized clinical trial. Estimating a possible loss of 15%, 192 patients are recruited. They will be distributed in two time-groups (2 and 1 minute) and in three propofol dose-subgroups (2, 1.5 and 1 mg/kg) as seen in table 1. The distribution in groups is done with a computerized randomizer that assigns each patient (1-192) to each group. Data collection begins consecutively until the sample size is reached.

*Table 1. Study groups*

Group	Time to propofol (min)	Propofol dose (mg/kg)
1	2	2
2		1.5
3		1
4	1	2

5		1.5
6		1

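### Unexpected difficult airway is an exclusion criterion, yet it can be met only after randomisation, when the pre-intubation outcomes are normally already recorded

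*Combined protocol and SAP*

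**What the plan says.** The exclusion list under Subjects contains "Predictors, known or unexpected difficult airway", so all three kinds of difficulty are treated as one eligibility rule.

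Under Design, a computerised randomiser "assigns each patient (1-192) to each group", and the sample size is given as "Estimating a possible loss of 15%, 192 patients are recruited".

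The Action protocol and the section on data collection fix the order of events:

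1. Baseline pressure and heart rate, then fentanyl.
2. The assigned wait of 1 or 2 minutes, then the assigned propofol dose.
3. Time to BIS below 60, with extra propofol if BIS is not reached in 2 minutes. SBP1/HR1 are noted once BIS is below 60.
4. Rocuronium, manual ventilation, laryngoscopy and intubation.
5. SBP2/HR2, 15 seconds after the tube is in place.

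The aims cover both sides of intubation. The Hypothesis speaks of "thus avoiding the pre-intubation hypotension and postintubation hypertension". The general objective asks whether "fewer hemodynamic changes related to orotracheal intubation occur". A specific objective is to "Evaluate hemodynamic variations after anesthetic induction according to the dose of propofol and the time since administration of fentanyl", and time to hypnosis is both an objective and the subject of the Kaplan-Meier comparison.

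The Statistical methods section names no analysis population. No section says how a patient who meets an exclusion criterion after randomisation is handled, or whether such a patient is replaced.

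**The concern.** An eligibility criterion should be decidable before allocation. This one, for its third category, is decided after allocation and after treatment, so it works as a post-treatment exclusion. Two things are at stake.

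- **Valid data.** Pre-intubation hypotension, haemodynamic variation after induction and time to hypnosis are normally settled before the laryngoscope is used. Dropping a patient for what happens afterwards discards a valid randomised observation. In the Kaplan-Meier comparison it normally discards an observed event. For these outcomes the exclusion gains nothing.
- **Protection of the comparison.** Difficulty is not defined, and the methods describe no blinding of the operator. The decision to remove a patient could thus be made by someone who knows the group. This does not show that removals would differ by arm, but the plan has no safeguard against it.

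**Working it through.** **Order of events.** The documents do not state when randomisation takes place, but the group must be known by the time propofol is due. Difficulty that was neither predicted nor known shows itself at manual ventilation or laryngoscopy, which is step 4. Set against the recorded variables:

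| Variable | Recorded at | Can a later difficult intubation change it? |
|---|---|---|
| Time to BIS below 60 | step 3 | no |
| Extra propofol | step 3 | no |
| SBP1/HR1 | step 3 | no |
| SBP2/HR2 | step 5 | yes |

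If ventilation difficulty were noticed before BIS fell below 60, it would still come after allocation.

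**The plan's own figure.** No alpha, power, SD or effect size is given, so 192 cannot be rebuilt from first principles. The loss step can be checked: with six equal groups (an assumption), 27 / 0.85 = 31.8, rounded up to 32, and 6 × 32 = 192. The allowance is 192 × 0.15 = 28.8 patients, leaving 163.2.

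**Number affected.** The documents give no rate of unexpected difficulty, so p below is an assumption. Patients affected = 192 × p. If they are removed and not replaced, the standard error is multiplied by √(1/(1 − p)). If they are replaced, precision is unchanged.

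| Assumed p | Patients of 192 | Per group of 32 | Rise in SE |
|---|---|---|---|
| 1% | 1.9 | 0.3 | 0.5% |
| 2% | 3.8 | 0.6 | 1.0% |
| 5% | 9.6 | 1.6 | 2.6% |
| 10% | 19.2 | 3.2 | 5.4% |

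All four rates fit within the allowance of 28.8. Even at 1%, the chance of at least one such patient is 1 − 0.99^192 = 85%, so the rule would probably be called on.

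**SBP2/HR2, keep or remove.** Let g be the mean difference, in SD, between patients with and without unexpected difficulty (also an assumption). Keeping these patients multiplies the SD by √(1 + p(1 − p)g²):

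- p = 2%, g = 0.5: √(1 + 0.0196 × 0.25) = 1.002
- p = 10%, g = 1.5: √(1 + 0.09 × 2.25) = 1.097

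Keeping and removing are equally precise when 1 + p(1 − p)g² = 1/(1 − p), that is, when g = 1/(1 − p): 1.02 SD at 2%, 1.05 at 5% and 1.11 at 10%. Below that gap keeping is more precise; above it removal is. Precision alone does not settle the choice for SBP2/HR2.

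**The case against.** **The documents never say that recorded data are deleted.** This stands. A reader might infer that the plan orders valid data to be thrown away, but the text does not go that far. What it does contain is an explicit exclusion rule, and no analysis population that would keep these patients in. The missing analysis population affects every post-randomisation loss, but here a written criterion points towards removal.

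**The numbers are small and the 15% allowance covers them.** This is correct for precision at the assumed rates. The allowance concerns numbers only; neither it nor replacement makes a post-treatment exclusion unbiased.

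**Bias is not shown.** This also stands. A reader might infer that the treatment contrast, especially for SBP2, would be distorted. That would require the assigned interval or dose to change how often difficulty arises, how it is judged or what effect it has. The documents give no evidence of this. Rocuronium is given in every group at the same dose after hypnosis is assessed, and there is one operator. A chance imbalance is not a systematic error.

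**For SBP2/HR2, exclusion may be reasonable.** The general objective concerns changes related to intubation, and a difficult intubation may alter those values. Limiting that question to uncomplicated intubations is a legitimate target if it is stated in advance. This argument does not reach the pre-intubation outcomes.

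**Other exclusions might be thought to share the fault.** A reader might extend the point to "Airway management with other supraglottic devices". Beside the inclusion criterion "Requiring general anesthesia with tracheal intubation", planned use is the natural reading, so the point is not extended to it.

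**Conclusion.** The point holds for the word unexpected in the airway criterion. As an exclusion it can be met only after randomisation and normally after the assigned treatment. Applied as written, with no analysis population defined, it would remove patients from outcomes that a later difficult intubation cannot affect.

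The size is modest: about 2 to 19 of 192 patients and a 0.5% to 5.4% rise in standard error without replacement, at assumed rates of 1% to 10%. Bias by arm is possible but not established, and no figure is put on it. For SBP2/HR2 either choice of main analysis is defensible. The change is worth making because it costs almost nothing and avoids a needless post-treatment exclusion.

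**What to change.** 1. Limit the eligibility exclusion to predicted or known difficult airway.
2. State that every randomised patient who received propofol is analysed in the assigned group for time to BIS below 60, SBP1/HR1 and extra propofol. Receipt of propofol is itself a condition met after randomisation, but without it there is no time to hypnosis as the Action protocol measures it.
3. Record unexpected difficult airway as a defined data field and report its number by arm.
4. Report SBP2/HR2 both with and without these patients, and state in advance which is the main analysis. Where no tube is placed, treat SBP2/HR2 as missing.

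The cost is one data field, one extra analysis and a few sentences of text, with no extra patients. If these patients are kept in the main SBP2/HR2 analysis, its SD rises by about 0.2% to 9.7% for assumed rates of 2% to 10% and gaps of 0.5 to 1.5 SD. Above a gap of about 1.0 to 1.1 SD, keeping them costs more precision than removing them would.

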## Methods

### Design

This is a prospective and randomized clinical trial. Estimating a possible loss of 15%, 192 patients are recruited. They will be distributed in two time-groups (2 and 1 minute) and in three propofol dose-subgroups (2, 1.5 and 1 mg/kg) as seen in table 1. The distribution in groups is done with a computerized randomizer that assigns each patient (1-192) to each group. Data collection begins consecutively until the sample size is reached.

*Table 1. Study groups*

Group	Time to propofol (min)	Propofol dose (mg/kg)
1	2	2
2		1.5
3		1
4	1	2

5		1.5
6		1

### Action protocol

On the day of the surgery, it is verified that the patient accepted the participation and has signed the informed consent. Confirmation of suspension or administration of usual medication indicated in the preoperative evaluation is performed.

The patient is monitored with a 5-lead electrocardiogram, pulse oximetry, non-invasive blood pressure cuff to the Dräger Infinity Delta monitor and Bispectral Index (BIS) monitor (Covidien Complete Monitor System P/N 185-0151, 2016, USA).

In case the patient don't have a venous access previously channeled, a peripheral variable-gauge venous cannula is placed according to the type of intervention (22-18 gauge).

Without prior fluid loading, but with a perfusion of 0.9% physiological solution at 100 ml/h, pre-oxygenation is carried out through a facial mask with 100% O2 until the expired fraction of O2 in the respirator gas analyzer (Dräger Primus, Germany) exceeds 80%. Once this point is reached, fentanyl 2 µg/kg is administered intravenously and, depending on the group to which the individual belonged (1, 2 and 3 or 4, 5 and 6), hypnotic is given after 1 or 2 minutes.

According to the corresponding group, 1, 1.5 or 2 mg/kg of propofol are administered, with intravenous lidocaine 0.5 mg/kg, and the time elapsed until the BIS drop below 60 is determined. When BIS does not reach the level of hypnosis after 2 minutes an extra dose of 0.5 mg/kg of propofol is administered. Subsequently, rocuronium 0.6 mg/kg is given and patient is maintained with manual ventilation until orotracheal intubation (Mackintosh # 3-4 laryngoscope).

In the case of hypotension: SBP <90 mmHg, SBP fall >30% or mean blood pressure (MBP) <60 mmHg; vasoactive drugs (VAD) (ephedrine or phenylephrine equivalent doses) are administered. In the presence of bradycardia (heart rate -HR- fall >30% or HR <50 bpm), atropine 0.1 mg/kg is administered intravenously.

### Statistical methods

Statistical analysis is performed using the Statistical Package for Social Sciences program (IBM SPSS Inc., USA) version 22 for Windows. For the descriptive statistics, central tendency and dispersion indices were used for the qualitative and quantitative variables. Confidence intervals were estimated with a 95% confidence level.

Age, weight, BIS, time at BIS less than 60, blood pressure, HR and reduction percentages of the BP and HR are treated as continuous quantitative variables. The remaining variables, such as sex, ASA risk (low: I and II – high: III and IV), antihypertensives, beta blockers or calcium blockers treatment, VAD and extra dose of propofol requirements are considered dichotomous quantitative variables. Study groups and age groups are classified as categorical variables.

For inferential statistics, normality is evaluated with Kolmogorov-Smirnov test and, in case of normal distribution, the results are expressed as arithmetic mean ( $\bar{x}$ ) and standard deviation (DS). In the absence of normality, the data are expressed in median (M) and interquartile range (IQR). For quantitative variables, if the data presents a normal distribution, a T student test is used. In cases with no normality criteria, Mann-Whitney U test. In qualitative variables, Chi-square and Fisher's exact test are used if more than 20% of the expected frequencies in the tables have a value less than 5. Finally, for comparisons of qualitative variables with quantitative variables, ANOVA or Kruskal-Wallis are used. To compare time to hypnosis between the groups, Kaplan-Meyers curve is used.

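### The first specific objective is most naturally read as asking whether age modifies the time-dose effect, but the plan specifies no test of that interaction and leaves its age groups undefined

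*Combined protocol and SAP*

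**What the plan says.** Under Objectives, Specifics, the first item is: "Assess whether the patient's age is a determining factor in hemodynamic variations dependent on time-dose".

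Statistical methods gives age two roles. It opens its list of continuous variables with age: "Age, weight, BIS, time at BIS less than 60, blood pressure, HR and reduction percentages of the BP and HR are treated as continuous". It then adds: "Study groups and age groups are classified as categorical variables". The number of age groups, their boundaries, and the analysis in which each form of age is used are not stated.

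The comparison methods named in that section are:
- for quantitative variables, "For quantitative variables, if the data presents a normal distribution, a T student test is used", with Mann-Whitney U if normality fails;
- "In qualitative variables, Chi-square and Fisher's exact test are used", the latter when expected counts are small;
- "Finally, for comparisons of qualitative variables with quantitative variables, ANOVA or Kruskal-Wallis are used";
- Kaplan-Meier curves for time to hypnosis.

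No regression, covariate adjustment, two-way model or interaction term appears anywhere. The Design section describes two intervals crossed with three propofol doses and 192 patients, allowing for 15% loss. It gives no effect size, SD, power or test alpha.

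**The concern.** Whether blood pressure response differs by age is one question. Whether age changes the effect of the interval or the dose is another. The objective's wording points to the second. The analysis section offers tools that, as described, compare an outcome across one grouping, which addresses the first. A significant difference between age groups could then be reported as the answer to the objective although nothing about time or dose had been tested.

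Two further problems come with the age groups. Cutting a continuous variable into groups discards information and so lowers power. Leaving the cut-points open also allows the split to be chosen after the data are seen, and the error rate then depends on how many splits were tried.

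**Working it through.** **Inputs from the documents.** 192 patients, 15% loss, two intervals by three doses (Design). 95% confidence level (Statistical methods), taken here as two-sided alpha 0.05.

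**Assumptions, because the documents are silent.** Equal allocation, normally distributed age, residual SD 1, and an age-by-interval interaction (difference in age slope between the two intervals) of 0.2 to 0.6 residual SD per SD of age.

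**The plan's own figure.** 192 × 0.85 = 163.2, and 163 / 0.85 = 191.8, which rounds up to 192. So 192 is consistent with 163 evaluable patients. The 163 itself cannot be reproduced without an effect size, SD and power. For six equal cells I use 27 per cell: 6 × 27 = 162.

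**Step 1: does a comparison across age groups answer the objective?** Simulated one-way ANOVA over age tertiles, N = 162:

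| True situation | Rejection rate |
|---|---|
| Age main effect 0.3 SD per SD, no interaction | about 85% |
| Interaction 0.45, age effect at one interval only | about 57% |
| Interaction 0.45, opposite age slopes at the two intervals | 4–5% |

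The first row has no effect modification and usually rejects. The third has real effect modification and rejects at chance level. The test therefore does not separate the two cases.

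**Step 2: information kept when a normal age is grouped.** The share kept is the variance of the group means divided by the total variance. For a median split this is 2/π = 0.637. For tertiles it is 0.793, and for four equal groups 0.861.

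**Step 3: power for the age-by-interval interaction.** An approximate check for continuous age: the expected z is β × √(N × 0.25), because an interval coded ±0.5 has variance 0.25. With N = 162, √40.5 = 6.364. At β = 0.45, z = 2.864, and power ≈ Φ(2.864 − 1.96) = Φ(0.904) ≈ 82%. A median split multiplies z by √0.637 = 0.798, giving 2.285, and power ≈ Φ(0.325) ≈ 63%. Simulation, which allows for estimated variance and varying age samples, gives:

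| Interaction (SD per SD of age) | Continuous age | Median split | Tertiles (2 df) |
|---|---|---|---|
| 0.2 | 24% | 18% | 17% |
| 0.3 | 45% | 32% | 30% |
| 0.45 | 79% | 62% | 60% |
| 0.6 | 96% | 83% | 84% |

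The loss from grouping runs from 6 points (24 − 18) to 19 points (79 − 60). Repeat simulations differ by about two to three points per cell.

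**Step 4: free choice of cut-point.** With no true interaction, age assumed normal with mean 55 and SD 16, and one two-group split chosen from 40, 50, 60, 65 or 70 years, at least one of the five interaction tests is significant in about 17–19% of trials. With continuous age the rate is about 5%.

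**The case against.** A reader might infer that the plan cannot test the interaction, or contains only one-factor tests. The text does not go that far. ANOVA is not labelled one-way, and a factorial ANOVA with age group as a factor is not excluded. Pairing ANOVA with Kruskal-Wallis suggests a single grouping, but that is inference. What stands is that no interaction test is specified.

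The objective can also be read differently: age as a determinant of the changes that follow these regimens, without effect modification. One-factor comparisons would partly address that. Effect modification remains the more natural reading of a phrase that ties the changes to time and dose, but it is not the only one.

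A reader might take the power figures as what will happen if the plan is followed. They are not. They price the grouping of age inside an interaction model that the plan does not name, under assumed effects. The two-group figures may also fit poorly: the plan calls two-level variables dichotomous and age groups categorical, which hints at more than two groups. Part of the tertile loss comes from the 2-df test. In simulation at 0.45, a 1-df trend test gave 69% over tertiles and 73% over quartiles, against 79% for continuous age. With small interactions the trial has low power however age is coded.

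Finally, this is one of five specific objectives, and the general objective does not mention age. That limits the weight of the point without removing it.

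**Conclusion.** The point holds as a failure to specify a suitable analysis, not as proof that none is possible. On its most natural reading the objective needs an age-by-interval or age-by-dose comparison, and none is named. Listing age as continuous does not help, because no listed method relates continuous age to an outcome.

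The mismatch between question and test does not depend on any assumed effect size: a comparison across age groups can reject without effect modification and fail to reject with it. The size of the power loss, about 6 to 19 points over the range shown, does rest on the assumed age distribution, interaction and grouping. The 17–19% error rate applies only if age is split in two and the cut is picked freely from the five listed. The change should be made before analysis, but it does not affect the trial's general objective.

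**What to change.** For percent change in SBP at preintubation and at post-intubation, and likewise for HR and MBP, specify a linear model with interval, dose as a factor, interval-by-dose, the baseline value, continuous age, age-by-interval and age-by-dose. Answer the objective from the interaction estimates with 95% CIs.

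Control the number of tests. Two interactions at two time points make four tests per outcome. If they were independent, the chance of at least one false positive would be 1 − 0.95⁴ = 18.5%, about as large as the cut-point problem. Either label the analysis exploratory, or use one joint test of the age interactions per outcome (1 df for interval plus 2 df for dose = 3 df) with one outcome named as main. The exploratory label is also apt because 192 is not shown to be powered for this question.

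Check the linearity of age with a quadratic or spline term. Use age groups for display only, with their number and cut-points fixed before analysis. State in the objective that effect modification is meant, if it is.

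The cost is a few sentences in Statistical methods and a little more analysis work. Age, SBP and HR are already recorded and MBP is already derived, so no new data or patients are needed. The downside is the linearity assumption for age, which the check above addresses.

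### Free improvement: interval and propofol dose are randomised as crossed factors, but the analysis names neither; a two-factor model with the recorded baseline would separate them

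*Combined protocol and SAP*

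**What the plan says.** - The Design section crosses two factors: "They will be distributed in two time-groups (2 and 1 minute) and in three propofol dose-subgroups (2, 1.5 and 1 mg/kg"). Table 1 numbers the six resulting groups.
- The general objective joins the factors: it asks whether fewer haemodynamic changes occur "by increasing the time elapsed between the administration of fentanyl and propofol and decreasing the dose of the latter". A specific objective asks about each: "Evaluate hemodynamic variations after anesthetic induction according to the dose of propofol and the time since administration of fentanyl". The Hypothesis section says that the dose needed depends on the interval.
- In Statistical methods, treatment appears once: "Study groups and age groups are classified as categorical variables". For quantitative outcomes, "if the data presents a normal distribution, a T student test is used", with Mann-Whitney otherwise; then "for comparisons of qualitative variables with quantitative variables, ANOVA or Kruskal-Wallis are used". The groups being compared are not named.
- Baseline pressure and heart rate are recorded before fentanyl (Data collection and study variables), but they enter the analysis only because "reduction percentages of the BP and HR are treated as continuous quantitative variables". Raw pressure and heart rate are also listed as continuous variables.
- "To compare time to hypnosis between the groups, Kaplan-Meyers curve is used". No test or model accompanies the curves.

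**The concern.** A crossed design can estimate the effect of the interval, the effect of the dose, and whether one depends on the other. The plan does not say that any of these will be estimated. At least three analyses fit its wording: a six-group test, a t-test of the two pooled time-groups with ANOVA by dose, and a factorial ANOVA. They answer different questions with different power, and the choice could be made after the data are seen.

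Under the six-group reading, a significant result may come from propofol dose alone and say nothing about the interval. If normality is rejected, the fallback tests cannot estimate two factors or their interaction, so the result of a normality test could remove the factorial analysis. The baseline values could sharpen every comparison but are used only as a divisor. The comparison of time to hypnosis is left at group level, although the hypothesis concerns the dose needed to reach anaesthetic depth.

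**Working it through.** **Inputs.** From the Design section: 192 patients, 15% loss, six cells. Equal allocation is assumed, because the ratio is not stated. 192 × 0.85 / 6 = 27.2, so 27 per cell and N = 162. The plan gives no test alpha, SD, effect size or correlation, so 192 cannot be re-derived. I assume two-sided 5%, effects in SD units, and a baseline–outcome correlation r of 0.3 to 0.7.

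**Interval effect d, power from the noncentral F.** Noncentrality is λ = 81d²/2, with 156 error df. At d = 0.443, λ = 81 × 0.196 / 2 = 7.95.

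| d (SD) | Two-factor model, 1 df | Six-group ANOVA, 5 df |
|---|---|---|
| 0.3 | 48% | 26% |
| 0.443 | 80% | 54% |
| 0.6 | 97% | 84% |

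Simulated Kruskal-Wallis over six groups gives 51% at 0.443 SD.

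**Pooled t-test, 81 v 81.** Dose differences stay in the error term. With dose means at +s, 0 and −s, λ becomes 7.95 / (1 + (2/3)s²). At d = 0.443, power is 80% for s = 0, 79% for s = 0.2, 76% for s = 0.4 and 71% for s = 0.6.

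**Dose effect only, no interval effect.** With a 2 v 1 mg/kg difference t and the middle dose halfway, the six-group test has λ = 27t². Group 3 v group 4 has λ = 27t²/2.

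| t (SD) | Six-group ANOVA rejects | Group 3 v group 4 rejects |
|---|---|---|
| 0.6 | 64% | 59% |
| 0.8 | 90% | 83% |
| 1.0 | 99% | 95% |

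Neither test can therefore be read as evidence about the interval.

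**Baseline as covariate, d = 0.443.** λ becomes 7.95 / (1 − r²). The percentage-reduction column is simulated in the same interval-by-dose model over six assumed settings (baseline mean 130–140, SD 15–25; outcome mean 105–150, SD 15–25 mmHg).

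| r | Raw outcome | Percentage reduction | Baseline covariate |
|---|---|---|---|
| 0.3 | 80% | about 61–75% | 84% |
| 0.5 | 80% | about 75–86% | 90% |
| 0.7 | 80% | about 93–97% | 98% |

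Repeat simulations moved the low ends of the percentage-reduction ranges down by one to two points.

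**What stays imprecise.** 80% power needs λ of about 7.95.
- Interaction (difference of the interval effects at two doses, variance 4/27): √(4 × 7.95 / 27) = 1.09 SD, or × √0.75 = 0.94 SD with baseline at r = 0.5.
- Group 3 v group 4 (variance 2/27): √(2 × 7.95 / 27) = 0.77 SD, or 0.66 SD with baseline at r = 0.5.
- An interval effect of 0.75 SD at one dose only averages to 0.25 SD. The averaged test then has 35% power, and the same-dose contrast has 78%.

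**Non-normal errors.** In simulations with skewed (lognormal) errors, the interval test's type I error was 4.6–5.3% with ordinary and 4.2–4.8% with robust standard errors. Skewness of that kind does not force a move to rank tests.

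**The case against.** The strongest reply is that the plan never commits to the six-group test. The t-test and Mann-Whitney are two-sample tests, and the Design section itself speaks of two time-groups with dose subgroups. A t-test by time-group and ANOVA by dose is an equally natural reading. It separates the factors, because randomisation crosses them, and it costs 0 to 4 points of power at dose steps up to 0.4 SD. This stands. A reader might infer that the plan loses 26 points of power (80% v 54%); the text does not support that, because the gap belongs to one permitted reading only.

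The baseline gain also depends on the comparator. Against raw pressure or heart rate at r = 0.3 it is 4 points, much less than against percentage reduction. This stands too, and both comparators are shown.

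A reader might also infer uncontrolled error from fifteen unadjusted group pairs (about 36% family-wise under the global null). The plan prescribes no such set of comparisons.

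What the reply does not remove is that the plan leaves the choice open, names no interaction although the hypothesis is about one factor depending on the other, and offers a non-normal route without a two-factor form.

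**Conclusion.** The point holds as an omission with a free remedy. The plan's tests are not invalid: under the pooled or factorial reading they address the interval properly. The plan does not say which comparison will be made, on which outcome, or how the two randomised factors will be separated.

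The size depends on the reading. At an assumed 0.443 SD interval effect, the two-factor model gains 26 points over a six-group ANOVA and 0 to 4 over the pooled t-test. Baseline adds a further 4, 10 or 18 points over the raw outcome at r = 0.3, 0.5 or 0.7. These figures rest on 27 per cell, equal allocation, two-sided 5%, and effect sizes and correlations that the plan does not give. The structural point needs no such assumption: a six-group overall test cannot say whether interval or dose produced a difference. This should be fixed before analysis.

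**What to change.** 1. For SBP, HR and MBP, before and after intubation, fit one linear model to all patients as randomised: outcome = interval + dose (three levels) + interval × dose + baseline value of that outcome. If residuals are clearly non-normal, use robust or bootstrap confidence intervals.
2. Report with 95% confidence intervals the interval effect averaged over doses, the interval effect at each dose, the dose effects and the interaction. Do not read a non-significant interaction as absence of one.
3. Before analysis, name one outcome, one time point and one contrast as primary, and treat the rest as secondary. Three outcomes at two time points give six tests of any contrast: 1 − 0.95⁶ = 26% family-wise error if they were independent, less if correlated. Use Holm or Tukey for pairwise contrasts.
4. Report group 3 v group 4 only as the combined-strategy comparison in the general objective, beside the separate effects.
5. Analyse time to BIS below 60 with a Cox model containing interval and dose, checking proportional hazards because extra propofol at 2 minutes may break them. Analyse extra-dose and vasoactive-drug requirement with logistic models in the same two factors, penalised or exact if events are few. Dose-stratified log-rank or Cochran-Mantel-Haenszel tests give no dose effect, so keep them as supplementary tests of interval.
6. Report hypotension only as seen at the recorded readings, since no hypotension event is listed among the variables. Show percentage reductions descriptively.

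**Cost.** A rewritten analysis section, with no new patients or data, and fewer results that can be called significant. Analysing as randomised includes any rescue treatment, which can dilute post-intubation pressure differences: an assumed 20 mmHg rise from vasoactive drugs in 20% v 10% of patients shifts the difference by 20 × (0.20 − 0.10) = 2 mmHg.
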